5% using ICSD-II diagnostic criteria. [1] Obstructive sleep apnoea in adolescents is largely unexplored, and the only publication on its prevalence has quite a few methodological flaws, namely small sample size and failure to represent the general population. [5]

It is well documented that childhood / adolescent OSA can lead to a variety of important sequelae which include cardiovascular, growth, neurocognitive and behavioural deficits together with metabolic disturbances. [6-9] Individuals with OSA have higher morbidity, mostly related to respiratory diseases and health care use starting from a young age. [14] They are also found to have poorer quality of life scores than healthy controls. [15] Therefore this proposal deals with an important condition that is currently insufficiently researched.

Two types of childhood OSA

Recent research has emphasized the “newer” type of childhood OSA, namely primarily obese subjects with only mildly enlarged lymphoid tissue. These obese children with OSA present differently and have distinct clinical phenotypic characteristics from non-obese children with OSA. [10] Different metabolic and immunological changes are present in obese children with OSA, and obesity can induce health changes that are independent from an isolated upper airway problem. Therefore the distinction between obese children with OSA from those of normal weight is very crucial. This newer type of childhood OSA is more akin to adulthood OSA as obesity is the major component in both. There is accumulating evidence that this type of childhood OSA begins in adolescence. [16]

Obstructive sleep apnoea in childhood usually remit by adolescence, and a large proportion of adolescents OSA cases are incident cases. Distinct risk factors for OSA are at play at each time point across paediatric ages, underscore the need to separate OSA research for children and adolescents. [16,17]

Why study adolescents?

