It is a cross-sectional, population-based study. Subjects who are found to meet all the inclusion and none of the exclusion criteria will be recruited. They will complete a set of sleep-related questionnaires, undergo anthropometric measurements, home polysomnographic (PSG) monitoring, attention assessment and phenotyping of their metabolic and cardiovascular risk.

Pilot Data and Sample Size Estimation

We have previously established a school-based cohort in 2003-2005 which included children aged between 6 and 13 years to determine the prevalence of OSA. [1] We then conducted a 4-year follow-up for a subgroup of the cohort was carried out. [25] At follow-up, the subjects were aged between 10 and 17 years. A total of 243 teenagers returned for the follow-up visit. The prevalence of OSA defined by different cut-offs and the minimum sample size required to detect corresponding prevalence with various levels of precision are presented in table 1. On further analysis those who returned for the 4-year follow-up had higher baseline OSA severity compared to the rest of the cohort [OAHl: 1.0 (0.1–2.5) c.f. 0.6 (0–2.0), $p=0.007$], therefore the calculated prevalence is likely an over-estimation. Nonetheless, using the proposed sample size would provide adequate power should the genuine population prevalence is lower than the calculated one.

Table 1. Minimum sample size required to detect the prevalence of OSA defined by various cut-offs with different levels of precision.

	OAHl $\geq 5/h$	OAHl $\geq 1/h$	OAHl $\geq 1/h$ + habitual snoring (ICSD criteria)
No. of cases	34/243	120/243	31/243
Prevalence	0.140	0.494	0.128
Precision			

	Minimum sample size required		
0.01	4623	9603	4276
0.015	2055	4268	1900
0.02	1156	2401	1069
0.025	740	1536	684
0.03	514	1067	475
0.04	289	600	267
0.05	185	384	171

In the current settings with limited budget allocation, our research team is capable of recruiting 740 adolescents to detect a prevalence of 14.0% with a precision of 2.5% (i.e. 95%CI: 11.5–16.5%) for the OAH1 \geq 5/h cutoff. The sample size can also ensure a precision of <4% for the OAH1 \geq 1/h cut-off and a precision of <2.5% for the ICSD criteria. [31] The sample size would also provide >99% power to detect the differences between the estimated prevalence of OSA in adolescents and the published prevalence of OSA in primary school children [1] no matter which cut-off is being used.

Sampling Frame

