The resultant prevalence will be compared to published prevalence of OSA in children. Logistic regression analysis will be used to identify possible risk factors of OSA in adolescents. Potential factors associated with a higher risk of OSA may include male sex, body weight, waist circumference, neck circumference, tonsil size, modified Mallampati score and chronotype. All these factors will be first assessed in univariate analysis. Those found to be significantly associated with OSA in univariate analysis will be assessed in multivariate model. The association between OSA and cardiovascular, metabolic and cognitive outcomes will be investigated. Comparisons will be made between subjects with and without OSA. Linear regression analysis will be conducted to assess the association between these outcomes and OAH. Multiple linear regression analysis will be performed to see if OAH is independently associated with these outcome measures while adjusting for possible confounders such as body mass index. The significant level will be set as $p < 0.05$. All analyses will be performed using SPSS version 20.0.

Feasibility and Timetable of Project

The proposed study will require a total of 30 months (130 weeks) to complete. We will be able to assess 8 subjects per week. For a sample size of 740, we will need 93 weeks for data collection. The first 12 weeks will be used for document preparation and school recruitment. The last 15 weeks will be used for data cleaning and analysis. The remaining 10 weeks should be allowed for clashes with schooling, missed appointments and public holidays.

Education plan

The principal investigator and the collaborator are all experienced teachers and supervisors. This project can further strengthen the educational activities and exchanges of the respective departments. It will also provide a good opportunity to train undergraduate and postgraduate students, especially for someone who is interested in the field of sleep medicine. The student will be provided with the required theoretical and practical training, and will work under close supervision of the principal investigator and related research personnel. This will allow the student to learn the knowledge and skills as a scientist, an ideal opportunity to advance himself / herself.

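### BMI adjustment is stated only for the continuous-OAHI linear model, not for the OSA yes/no comparisons or the diabetes, hypertension and metabolic syndrome outcomes

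*Combined protocol and SAP*

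**What the plan says.** The Statistical Analysis section gives three analyses of the cardiovascular, metabolic and cognitive outcomes.

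1. A group contrast: "Comparisons will be made between subjects with and without OSA". No test and no covariates are named.
2. A regression on the continuous index: "Linear regression analysis will be conducted to assess the association between these outcomes and OAH".
3. An adjusted version of the second: "Multiple linear regression analysis will be performed to see if OAH is independently associated with these outcome measures", carried out while "adjusting for possible confounders such as body mass index".

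One significance level, 0.05, is set for everything. The section does not call the group contrast descriptive and does not say which of the three analyses carries the conclusion. BMI is given as an example of a confounder, so the covariate list is open; age and sex are not named.

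The Abstract also lists the risk of diabetes, hypertension and metabolic syndrome among the secondary outcomes and mentions logistic regression. The Statistical Analysis section states no adjusted model for these binary outcomes.

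On background, the section on two types of childhood OSA says that "obesity can induce health changes that are independent from an isolated upper airway problem". Key Issues, item 3, describes one OSA type as mainly obesity-related and stresses that obese and non-obese subjects should be separated in OSA research.

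**The concern.** By the protocol's own account, adiposity is associated with the exposure (OSA) and, by a separate route, with metabolic and immune markers. That is the standard structure of confounding. A comparison of adolescents with and without OSA that leaves BMI out therefore mixes any OSA effect with the effect of a BMI difference between the groups.

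The adjusted OAHI model does not supply the missing estimate. A slope per unit of OAHI and a difference between diagnosed and undiagnosed adolescents are different quantities, and only the first has an adjusted version in the plan. If the group contrasts are reported with p-values, a difference in, say, leptin, lipids, hs-CRP or blood pressure could be read as a consequence of OSA when it reflects body size. The Education plan section says the results are meant to inform parents, clinicians and officials who allocate resources, so that misreading would matter.

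**Working it through.** **Inputs from the documents.** N = 740, prevalence 14.0% at OAHI ≥5/h and precision 2.5 points (Pilot Data and Sample Size Estimation); prevalence 49.4% at OAHI ≥1/h (Table 1); significance level 0.05, taken as two-sided because sidedness is not stated.

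**Reproducing the plan's figure.** n = 1.96² × 0.14 × 0.86 / 0.025² = 740.02, which matches 740. The documents give no power, effect size or error rate for the group contrasts, so there is nothing further to reproduce.

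**Assumptions not in the documents.** OSA has no effect of its own. Cases have a mean BMI z score higher by d SD, with d from 0.3 to 0.8. Each outcome has correlation r with BMI z score, with r from 0 to 0.5. School clustering is ignored because no intraclass correlation is given.

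**Formula.** Cases: 0.14 × 740 ≈ 104; non-cases: 636. The standard error of a standardised difference is √(1/104 + 1/636) = 0.106 SD. BMI alone produces a difference of r × d. The chance of significance is P(|Z + r·d/SE| > 1.96).

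Example: d = 0.5, r = 0.3 gives 0.15 / 0.1058 = 1.418, and Φ(1.418 − 1.96) + Φ(−1.418 − 1.96) = 0.29.

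**Results, 104 v 636:**

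| BMI gap d | r = 0 | r = 0.1 | r = 0.3 | r = 0.5 |
|---|---|---|---|---|
| 0.3 SD | 5% | 6% | 14% | 29% |
| 0.5 SD | 5% | 8% | 29% | 66% |
| 0.8 SD | 5% | 12% | 62% | 97% |

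**Sensitivity to the number of cases, at r = 0.3.** The protocol says its pilot prevalence is probably too high. At an assumed 5% prevalence (37 v 703) the rates for gaps of 0.3, 0.5 and 0.8 SD are 8%, 14% and 30%. At the OAHI ≥1/h cut-off (366 v 374) they are 23%, 53% and 90%.

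**How many outcomes?** Take 14 outcomes with illustrative correlations: one at 0, four at 0.1, two at 0.2, four at 0.3, two at 0.4 and one at 0.5. With 104 v 636, the expected number significant is the sum of the individual rates: 1.7 for a gap of 0.3 SD, 3.4 for 0.5 SD and 6.3 for 0.8 SD. By chance alone it is 14 × 0.05 = 0.7.

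**Effect of the fix.** In simulations of 104 v 636 with no OSA effect (4,000 runs each; d = 0.3, 0.5, 0.8; r = 0 to 0.4), adding BMI as a covariate kept the rejection rate between 4.3% and 5.4% throughout. The unadjusted rate in the same scenarios ran from about 5% to 86%. The simulations cover continuous outcomes only and assume that BMI acts linearly.

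**The case against.** The strongest reply is that the same paragraph already deals with BMI. It moves from a crude comparison to a model whose stated purpose is to test independent association with BMI adjusted for, and it reserves the idea of independence for that step. Outcome Measures defines the secondary outcome as correlation with OSA severity, and the Education plan describes the expected results in the same terms. OAHI measures severity, so the adjusted OAHI model fits the stated aim. The group contrast names no covariates, but it does not exclude them either. A crude difference in means is also a real difference; it misleads only if it is taken as an effect of OSA.

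Much of this stands. A reader might infer that the plan overlooks BMI confounding; it does not. A reader might also infer that higher BMI among cases will by itself make many of these comparisons significant. The documents do not support that. They give no BMI gap between the groups and no BMI-outcome correlations; one of the two OSA types they describe occurs without obesity, which would narrow the gap; and they give no link between BMI and the continuous performance test.

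What the reply does not remove is that the yes/no contrasts come under the general significance threshold with neither adjustment nor a descriptive label, that no adjustment is stated for the Abstract's binary outcomes, and that the plan does not say which analysis decides.

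**Conclusion.** The point holds in a limited form. As written, the OSA yes/no contrasts can reach significance through BMI alone for outcomes related to BMI, and the planned adjusted model yields no adjusted estimate for the diagnosis itself. At a correlation of 0.3 with 104 v 636, the false-positive rate is about 14% to 62% for BMI gaps of 0.3 to 0.8 SD, against a nominal 5%. It falls if there are fewer cases, rises at the OAHI ≥1/h cut-off, and stays at 5% for outcomes unrelated to BMI.

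The direction of the problem follows from the protocol's own reasoning about obesity. Its size rests entirely on the assumed gaps and correlations. This concerns secondary analyses; the prevalence estimate is not affected. The change is still worth making because it removes a foreseeable bias at almost no cost.

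**What to change.** Amend the Statistical Analysis section as follows:

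- Run each OSA yes/no contrast as a linear model (logistic for diabetes, hypertension and metabolic syndrome) with age, sex and BMI z score as covariates.
- Use the same fixed covariates in the OAHI model, replacing the open-ended list.
- State that conclusions rest on the adjusted estimates and that unadjusted comparisons are descriptive only.

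This takes a sentence or two of wording. BMI z score is already planned under Collection of Data, and age and sex need no additional measurement.

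The downside is slightly wider intervals where BMI and OSA are correlated. For a continuous outcome, and counting BMI alone, the standard error is multiplied by about √(1 + d² × 0.14 × 0.86): 1.015 at d = 0.5 and 1.04 at d = 0.8. For outcomes related to BMI this is offset by a smaller residual SD (a factor of √(1 − 0.3²) = 0.95 at r = 0.3).
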